1. LIST OF ABBREVIATIONS

AE	Adverse Event
AROM	Active Range of Motion
CFR	Code of Federal Regulations
CI	Confidence Interval
CRF	Case Report Form
DOMS	Delayed Onset Muscle Soreness
ECDF	Empirical Cumulative Distribution Function
GCP	Good Clinical Practice
GROC	Global Rating of Change
HRR	Heart Rate Recovery
HSP	Human Subjects Protection
ICH	International Council for Harmonisation
IMSO	International Musculoskeletal Organisation
IREB	Institutional Review and Ethics Board
ISRCTN	International Standard Randomised Controlled Trial Number
LEFS	Lower Extremity Functional Scale
LOCF	Last Observation Carried Forward
MCID	Minimal Clinically Important Difference
M.O.V.E.	Movement-Oriented Velocity of Engagement
MSK	Musculoskeletal
NIH	National Institutes of Health
NRS	Numeric Rating Scale
ORCID	Open Researcher and Contributor ID
QA	Quality Assurance
RCT	Randomized Controlled Trial
RPE	Rating of Perceived Exertion
SAE	Serious Adverse Event
SD	Standard Deviation
SLS	Single-Leg Stance
SOP	Standard Operating Procedure
STS	Sit-to-Stand
UEFI	Upper Extremity Functional Index
WHO	World Health Organization

2. PROTOCOL SYNOPSIS

Title:

A Prospective, Multi-Site, Interventional Case-Series to Evaluate the M.O.V.E. Protocol for the Management of Acute and Subacute Musculoskeletal Conditions.

Study Design:

A prospective, multi-site, single-arm, interventional case-series with an 8-week follow-up period. This study serves as a feasibility and pilot investigation.

Population:

Adults aged 18-70 with acute or subacute (<12 weeks) musculoskeletal pain of mechanical origin, with a baseline pain score of ≥ 4 on a 0-10 Numeric Rating Scale (NRS).

Intervention:

The M.O.V.E. (Mobilize, Optimize, Validate, Energize) protocol, a criterion-based, progressive activity and mechanotherapy program delivered over 8 weeks.

Primary Objective:

To assess the feasibility and safety of the M.O.V.E. protocol and to evaluate its effect on pain reduction.

Primary Endpoint:

Change in pain intensity from Baseline to Week 8, as measured by the Numeric Rating Scale (NRS).

Secondary Endpoints:

- Change in function (LEFS/UEFI)
- Change in balance (SLS)
- Change in functional strength (STS)
- Global Rating of Change (GROC)
- Time to return to Activities of Daily Living (ADL)
- Adherence to the protocol
- Incidence of Adverse Events (AEs)

Sample Size:

A pragmatic sample of approximately 40 participants will be recruited across 5 international sites for this feasibility study.

Study Duration:

Each participant will be in the study for 8 weeks.

3. INTRODUCTION: BACKGROUND & RATIONALE

Musculoskeletal (MSK) conditions represent a leading cause of disability worldwide, imposing a significant burden on individuals and healthcare systems. Traditional management for many acute and subacute MSK injuries has often included periods of rest, immobilization, and modalities such as icing (cryotherapy). However, a growing body of evidence suggests that this approach may be suboptimal [1]. Prolonged rest can lead to muscle atrophy, joint stiffness, and impaired neuromuscular control, while the routine use of cryotherapy is being questioned for its potential to blunt the natural inflammatory and regenerative processes essential for optimal tissue healing [2].

This paradigm shift is rooted in the principles of mechanotransduction, the process by which cells convert mechanical stimuli into biochemical responses [3]. Early, controlled loading and movement provide the necessary signals to guide the organization and remodeling of healing tissues, such as collagen fibers in tendons and ligaments. The absence of these mechanical signals can result in disorganized, weaker scar tissue and a delayed functional recovery.

The M.O.V.E. (Movement-Oriented Velocity of Engagement) protocol is a structured, multi-faceted intervention designed to operationalize these modern principles. It represents a departure from the passive, rest-focused model towards an early, criterion-based application of progressive activity. The protocol is built on four interdependent pillars:

1. Mobilize: Initiates early, pain-free movement to reduce arthrogenic muscle inhibition, improve synovial fluid circulation, and maintain neural pathway integrity.
2. Optimize: Applies progressive mechanical loads to stimulate tissue adaptation and remodeling, moving systematically from isometric to complex functional movements based on tissue tolerance.
3. Validate: Focuses on restoring neuromuscular control, proprioception, and balance to ensure that movement quality is high and compensatory patterns are minimized.
4. Energize: Incorporates low-intensity cardiovascular activity to enhance systemic circulation, improve metabolic efficiency, and support the energetic demands of tissue repair and recovery.

This prospective, multi-site case-series (MOVE-001/2025) is designed as a crucial first step to formally evaluate the feasibility, safety, and preliminary efficacy of the M.O.V.E. protocol in a real-world clinical setting across diverse patient populations and international sites. The findings will provide the foundational data required to design future large-scale randomized controlled trials (RCTs).

4. STUDY OBJECTIVES AND ENDPOINTS

4.1 PRIMARY OBJECTIVE

To assess the feasibility of implementing the M.O.V.E. protocol across multiple clinical sites and to evaluate its preliminary efficacy in reducing pain in individuals with MSK conditions.

Primary Endpoint:

Change in Pain (NRS): The absolute change in the 11-point Numeric Rating Scale (NRS) for pain from Baseline to Week 8. A Minimal Clinically Important Difference (MCID) is defined as a reduction of ≥ 2 points [4].

4.2 SECONDARY OBJECTIVES

- To evaluate the effect of the M.O.V.E. protocol on physical function, balance, and strength.
- To assess patient-reported outcomes of recovery and treatment satisfaction.
- To characterize the safety profile of the intervention.
- To quantify patient adherence to the home-based components of the protocol.

Secondary Endpoints:

- Functional Improvement: Change in the Lower Extremity Functional Scale (LEFS) or Upper Extremity Functional Index (UEFI) score from Baseline to Week 4 and Week 8. The MCID is 9 points [5].
- Balance: Change in Single-Leg Stance (SLS) time (in seconds) from Baseline to Week 8.
- Functional Strength: Change in the number of repetitions completed in the 30-second Sit-to-Stand (STS) test from Baseline to Week 8.
- Global Perceived Effect: Score on the Global Rating of Change (GROC) scale at Week 8.
- Time to Recovery: Time (in days) from enrollment to return to full, unrestricted Activities of Daily Living (ADL) and, for a subset, return to sport.
- Adherence: Percentage of prescribed home exercise sessions completed, tracked via patient logs and verified by clinicians.
- Safety: Incidence, nature, and severity of all Adverse Events (AEs) and Serious Adverse Events (SAEs).

[figure not shown]
5. STUDY DESIGN

This is a prospective, multi-site, single-arm, interventional case-series designed to assess a standardized clinical protocol. The study will be conducted at five international sites, including academic labs, private clinics, and community-based centers.

Participants will undergo a screening and baseline assessment, after which they will receive the 8-week M.O.V.E. protocol intervention. Follow-up assessments will be conducted at Week 2, Week 4, and Week 8.

The study design was chosen to establish initial proof-of-concept, assess feasibility, and generate hypotheses for a subsequent, more definitive RCT. The single-arm design is appropriate for this early phase of investigation where the primary goal is to observe the response to a novel, standardized intervention.

Figure 1: Pain Trajectory - Preliminary data from an initial pilot cohort (n=6) showing the expected pain trajectory (see attached graphs).

6. SUBJECT SELECTION AND WITHDRAWAL

6.1 INCLUSION CRITERIA

1. Male or female, aged 18 to 70 years, inclusive.
2. Presenting with a primary complaint of musculoskeletal pain (e.g., lumbar strain, ankle sprain, shoulder impingement-related pain, patellofemoral pain).
3. Acute or subacute symptom duration of less than 12 weeks.

4. Baseline pain intensity of ≥ 4 on the 11-point NRS.
5. Able and willing to provide written informed consent and to comply with all study procedures and visits.

6.2 EXCLUSION CRITERIA

1. Presence of any "red flag" conditions requiring immediate medical referral (e.g., suspected fracture, cauda equina syndrome, tumor, systemic inflammatory disease).
2. Confirmed complete tissue rupture (e.g., Grade III ligament tear, complete tendon rupture).
3. Major or progressive neurological deficit.
4. Uncontrolled or unstable medical comorbidities (e.g., cardiovascular, metabolic, or psychological conditions) that would preclude safe participation in an exercise-based protocol.
5. Pregnancy.
6. Involvement in another interventional clinical trial concurrently or within the past 30 days.
7. Inability to understand and follow instructions in the primary language of the clinical site.

6.3 SUBJECT WITHDRAWAL

Subjects may be withdrawn from the study at any time for the following reasons:

- Voluntary withdrawal by the subject.
- A significant AE or intercurrent illness that, in the investigator's opinion, warrants discontinuation.
- Failure to adhere to protocol requirements.
- The investigator deems it is not in the subject's best interest to continue.

All withdrawn subjects will be followed up for safety outcomes, and the reason for withdrawal will be documented in the Case Report Form (CRF).

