9.2 SAMPLE SIZE DETERMINATION

As this is a feasibility and pilot study, a formal, power-based sample size calculation is not appropriate. A pragmatic sample size of approximately 40 participants ($n \approx 8$ per site) is considered sufficient to assess the feasibility of recruitment, protocol implementation, and to generate stable estimates of the means and variances of the outcome measures. These estimates will be used to power a future, definitive RCT.

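### Section 6.3 lets sites withdraw participants from the study itself and provides only for safety follow-up, so their Week 8 pain scores are likely to be lost selectively

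*Protocol*

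**What the plan says.** Section 6.3 of the protocol opens with "Subjects may be withdrawn from the study at any time for the following reasons". Four grounds follow. One is the participant's own decision. The site applies the other three: "A significant AE or intercurrent illness that, in the investigator's opinion, warrants discontinuation"; "Failure to adhere to protocol requirements"; and "The investigator deems it is not in the subject's best interest to continue". The section then states what happens next: "All withdrawn subjects will be followed up for safety outcomes, and the reason for withdrawal will be documented in the Case Report Form (CRF").

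The primary endpoint in Section 4.1 is "The absolute change in the 11-point Numeric Rating Scale (NRS) for pain from Baseline to Week 8", and Section 9.1 analyses it as a within-subject change, so a participant without a Week 8 score contributes no observed value. Section 4.2 makes adherence a secondary endpoint: "Percentage of prescribed home exercise sessions completed, tracked via patient logs and verified by clinicians". The schedule in Section 8.1 lists the NRS at baseline and Weeks 2, 4 and 8, and adherence log reviews at Weeks 2, 4 and 8. It has no rule for withdrawn participants. Section 9.2 says of the study's means and variances: "These estimates will be used to power a future, definitive RCT".

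**The concern.** The text treats stopping the exercise programme and leaving the study as one event. Once a site has withdrawn someone, the protocol requires safety follow-up and a recorded reason, but no further pain score. A later NRS is not forbidden; it is simply not provided for. A site working from the text would have no instruction to obtain one.

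The loss would not be random. Adverse events, non-adherence and investigator judgement all plausibly depend on how the participant is doing. The Week 8 change would then describe mainly those who tolerated and followed the programme. Adherence is affected more directly, because poor adherence can itself lead to removal, and the remaining log reviews would then not take place. The recorded reason shows who left and why, but not how their pain ended.

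This cannot be left to the statistical analysis plan. That document can choose a method for missing scores, but the protocol decides whether they are collected. Last observation carried forward appears in the abbreviation list and nowhere else in the protocol; even if used, it would only put an earlier score in place of the Week 8 one.

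**Working it through.** **Inputs from the protocol.** Five sites (Section 5) with about 8 participants each (Section 9.2); NRS from 0 to 10 (Section 2); MCID of 2 points (Section 4.1). The stated sample size reproduces: 5 × 8 = 40.

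**Inputs assumed.** The protocol gives no withdrawal rate, no difference in outcome between leavers and completers, and no SD. I take a withdrawn share f of 10–20% (4 to 8 of 40) and vary the gap in mean improvement (completers minus withdrawn).

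**Bias of the completer mean.** Let C be the mean improvement of completers and W that of withdrawn participants.

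- All-enrolled mean = (1 − f) × C + f × W
- Completer mean minus all-enrolled mean = f × (C − W) = f × gap

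| Gap (NRS points) | f = 0.10 (4 of 40) | f = 0.20 (8 of 40) |
|---|---|---|
| 3 | 0.3 | 0.6 |
| 2 | 0.2 | 0.4 |
| 0 | 0 | 0 |
| −1 (withdrawn improve more) | −0.1 | −0.2 |

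A positive value means the reported improvement is too favourable.

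**Bound that assumes only f.** For a participant with baseline score b, the Week 8 score lies between 0 and 10, so the reduction lies between b − 10 and b, a range of 10 points. With a share f missing, the all-enrolled mean change is undetermined over 10 × f:

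- 4 of 40 missing: 10 × 0.10 = 1.0 point
- 8 of 40 missing: 10 × 0.20 = 2.0 points, numerically equal to the MCID

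This is a limit, not an expected bias.

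**Precision, for comparison.** With an assumed SD of 2 to 2.5, the normal-approximation 95% CI half-width is 1.96 × SD / √n. At n = 40 it is 0.62 to 0.77; at n = 32 it is 0.69 to 0.87. The loss of precision is small. Selection is the main problem.

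**By site.** Section 9.1 compares sites by Cohen's d. With about 8 per site, one withdrawal removes 1/8 = 12.5% of a site's sample.

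**The case against.** The strongest reply is that silence is not a bar. Section 6.3 sets a minimum, withdrawal is optional, the Section 8.1 schedule exempts nobody, and the SOPs mentioned in Sections 10 and 16 may cover the matter. It is true that the loss is likely rather than certain. But those SOPs are not shown, and where a text names safety alone, collection of anything else would depend on the site.

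Second, the non-adherence ground may refer to visits and procedures rather than home exercise, and Section 7 describes a flexible programme that answers a flare by deloading. Fewer poor tolerators may therefore be withdrawn than one might fear. Under either reading, though, a participant removed on this ground leaves the study with safety follow-up only.

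Third, the size is assumed. This stands in full. Some of the assumed 10–20% would be voluntary, and where consent is withdrawn the proposed change recovers nothing, so on those inputs the figures are upper limits on what it could remove. The bound also ignores Week 2 and Week 4 scores that later leavers would have, and its ends need every missing score to be 0 or every one to be 10.

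Fourth, this is a descriptive single-arm pilot with no hypothesis test, and a shift of a few tenths of a point reverses no stated conclusion. That limits the seriousness. It does not remove the point, because the study's stated products are a feasibility assessment and estimates for planning a trial, and both depend on who is counted. No effect on the future trial's sample size has been shown here, and a single-arm mean change does not by itself supply a between-group difference.

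**Conclusion.** The concern holds. That Section 6.3 omits outcome follow-up after withdrawal is plain from the text, and nothing elsewhere in the protocol fills the gap. That Week 8 scores will be lost as a result is a likely consequence, not a certain one. The probable direction is an overstated improvement: 0.2–0.6 NRS points if 10–20% are withdrawn and improve 2–3 points less than completers. It could be nil, or an understatement of 0.1–0.2 points if leavers improve 1 point more. The withdrawal rate and the gap are both assumptions. It should be fixed before enrolment because the data cannot be recovered afterwards, but it does not undermine the design.

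**What to change.** Reword Section 6.3 to separate stopping the intervention from leaving the study:

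- Leave the grounds for stopping the intervention unchanged.
- State that non-adherence does not end outcome follow-up.
- Collect the NRS and the other patient-reported outcomes at the remaining scheduled visits through Week 8, by phone or online if needed, from everyone enrolled unless consent is withdrawn.
- Report the Week 8 change and adherence for all enrolled participants. The model and sensitivity analyses can stay in the statistical analysis plan.

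The cost is the wording and a few follow-up contacts: about 4 to 8 participants if 10–20% stop, an assumed rate. Section 6.3 already requires safety follow-up of these people, and the NRS is a single 0–10 rating. No extra participants are needed. Remote collection is a change in mode of assessment that the protocol does not now describe, so it should be written in and recorded. The mean change and the adherence figure may come out less favourable.

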7. STUDY INTERVENTION

The M.O.V.E. protocol is a multi-modal program administered over 8 weeks. It is not a rigid prescription but a criterion-based framework guided by patient tolerance and functional progression. All participating clinicians will undergo standardized training on the protocol's principles and application.

Domain	Prescription (Real-World)	Progression Gate
M -- Mobilize Early	Pain-free AROM, joint oscillations, breath-led mobility 5–10 min, 3–5×/day ; grade I–II tissue glides	No sharp/tearing pain; no swelling >24h; technique clean
O -- Optimize Load	Isometric → isotonic → tempo/eccentric; RPE 2–4 → 4–6; 2–3×8–15 ; 48-h flare rule	DOMS ≤48h; movement control; pain ≤3/10 during/after
V -- Validate Neural Control	Balance/proprioception, perturbations, step-downs, hop-prep 10–15 min/session	Stable mechanics (no valgus/collapse); task competence
E -- Energize Recovery	Nasal breathing + brisk walk/cycle, Zone 2–3, 20–30 min, 3–5 d/wk	HRR improving; no symptom spike >24h

MOVE DOSAGE & PROGRESSION GATES

Domain: M -- Mobilize Early

Prescription (Real-World): Pain-free AROM, joint oscillations, breath-led mobility 5–10 min, 3–5×/day; grade I–II tissue glides

Progression Gate: No sharp/tearing pain; no swelling >24h; technique clean

Domain: O -- Optimize Load

Prescription (Real-World): Isometric → isotonic → tempo/eccentric; RPE 2–4 → 4–6; 2–3×8–15; 48-h flare rule

Progression Gate: DOMS ≤48h; movement control; pain ≤3/10 during/after

Domain: V -- Validate Neural Control

Prescription (Real-World): Balance/proprioception, perturbations, step-downs, hop-prep 10–15 min/session

Progression Gate: Stable mechanics (no valgus/collapse); task competence

Domain: E -- Energize Recovery

Prescription (Real-World): Nasal breathing + brisk walk/cycle, Zone 2–3, 20–30 min, 3–5 d/wk

Progression Gate: HRR improving; no symptom spike >24h

PROGRESSION GATES AND DELOADING

Progression from one phase to the next within each domain is governed by explicit criteria (Progression Gates). If a patient experiences a symptom flare (e.g., pain increase >2 points on NRS lasting >24 hours, significant increase in swelling), a mandatory 48-hour deload is initiated, where activity is reduced to the last tolerated level.

8. STUDY ASSESSMENTS AND PROCEDURES

8.1 Schedule of Assessments

Assessment	Screening / Baseline (W0)	Week 2	Week 4	Week 8 (End of Study)
Informed Consent	X			
Inclusion/Exclusion Criteria	X			
Demographics & Medical History	X			
Primary Outcome				
Pain NRS	X	X	X	X
Secondary Outcomes				
LEFS / UEFI	X		X	X
Single-Leg Stance (SLS)	X			X
30-s Sit-to-Stand (STS)	X			X
Global Rating of Change (GROC)				X
Time to ADL / Sport	X	X	X	X
Adherence Log Review		X	X	X
Safety				
Adverse Event Monitoring	X	X	X	X

[figure not shown]

9.2 SAMPLE SIZE DETERMINATION

As this is a feasibility and pilot study, a formal, power-based sample size calculation is not appropriate. A pragmatic sample size of approximately 40 participants ($n \approx 8$ per site) is considered sufficient to assess the feasibility of recruitment, protocol implementation, and to generate stable estimates of the means and variances of the outcome measures. These estimates will be used to power a future, definitive RCT.

10. QUALITY CONTROL AND QUALITY ASSURANCE

To ensure the quality and integrity of the study data, the following measures will be implemented:

- Standard Operating Procedures (SOPs): All sites will operate under a common set of SOPs for participant recruitment, informed consent, data collection, and intervention delivery.
- Investigator Training: All site investigators and clinical staff will attend a mandatory study initiation meeting for comprehensive training on the protocol and all study procedures.
- Site Monitoring: A clinical research associate (CRA) will conduct on-site monitoring visits (initiation, interim, and close-out) to perform source data verification (SDV) on a subset of CRFs, ensure regulatory compliance, and resolve any queries.
- Centralized Data Management: All data will be entered into a centralized, secure, GCP-compliant electronic data capture (EDC) system. Automated edit checks will be built in to minimize data entry errors.

11. ETHICS AND REGULATORY COMPLIANCE

This study will be conducted in full compliance with the principles of the Declaration of Helsinki (2013), the International Council for Harmonisation (ICH) E6(R2) Good Clinical Practice guidelines, and all applicable national and local regulations (e.g., US DHHS 45 CFR 46).

11.1 INSTITUTIONAL REVIEW AND ETHICS BOARD (IREB)

The protocol, informed consent form, and all other relevant study documents will be submitted to the MMSx Authority central IREB for review and approval. The study will not commence at any site until written approval from the IREB has been obtained. Each site will also be responsible for obtaining approval from their local IRB/IEC, if required.

11.2 INFORMED CONSENT

Written, informed consent must be obtained from each participant before any study-specific procedures are performed. The informed consent process will be conducted by a qualified investigator or designee, who will explain the study's purpose, procedures, risks, and benefits in non-technical language.

11.3 CONFIDENTIALITY

All participant information will be kept strictly confidential. Participants will be assigned a unique identification number, and all study records and datasets will use this identifier. Documents linking names to identifiers will be stored separately in a secure, locked location.

12. DATA HANDLING AND RECORD KEEPING

Data will be collected on standardized paper or electronic Case Report Forms (CRFs). All source documents and CRFs will be retained at the investigational sites in a secure location for a minimum of 5 years after study completion, or as required by local regulations. An audit trail will be maintained for all data changes in the EDC system.

Data Availability: In accordance with open science principles, a de-identified dataset and the full statistical analysis plan will be made available upon reasonable request to the corresponding author, following publication of the primary results and with authorization from the IREB.

